Special issue #2: A potential loss of confidentiality - Performing research on this topic with a vulnerable population requires careful attention to ethical issues associated with confidentiality. This is particularly the case in communities where there is a history of exploitation and social and economic disparities, and an HIV diagnosis can be highly stigmatizing. We will adhere to strict guidelines regarding confidentiality, and ensure interviews with participants will be performed at a private location of the interviewees choosing. All family members and friends will be asked to wait in the waiting room while the interview is conducted. Participants’ HIV status will be kept in a secure file in the HIV testing area that can only be accessed by research and clinic staff, to document test results when no one else is present in the room. All study forms will be kept in locked file drawers, and immediately transcribed onto password-protected computers equipped with anti-virus software. All survey information and HIV test results will be linked by a de-identified patient number, to protect privacy. In addition, NHLS data will be stored in a protected data base, and will only be accessed to verify information related to ART uptake and/or mortality.

Special issue #3: Risk of interview fatigue – Given the in-depth nature of the proposed research, we will need to spend time interviewing clients during a time of potentially high stress for them. We will ensure that interviews last no more than 45-60 minutes with regularly scheduled breaks throughout the session. Participants will be informed in advance that they can take a break or stop at any time. Our RA has performed extensive qualitative research in the past, and is trained in assessing interviewee fatigue and will stop accordingly.

Special issue #4 - Discussion of sensitive topics– As part of our interview with these subjects, we will be discussing sensitive topics relating to HIV acquisition and stigma. This raises the question of trust that clients must be able to put into researchers in order to speak about these issues. Study personnel will undergo training to ensure interviews are performed in a non-judgmental manner.

Special issue #5 - Access to ART during the study: ART usage has clearly been shown to decrease morbidity and mortality, as well as decrease heterosexual transmission of HIV. For patients who refuse ART, it is our ethical duty to ensure that access to ART is optimized, and we provide a standard of care that provides free and accessible ART. All participants will be counseled on the benefits of ART and provided with direct referrals if they meet treatment criteria. While we recognize this may impact our findings, and possibly result in our underestimating the impact of our intervention due to a Hawthorne effect in the control arm, we believe that we have an ethical obligation to ensure refusers receive proper information, referral, and access to ART during the course of the study.

Special issue #6 – *Psychological Distress*: Participants may experience psychological distress resulting from the assessment questions. Using strategies established in our previous SA and US studies, including the pilot study (NYSPI IRB # 6848), steps will be taken to minimize the risk of psychological distress resulting from assessment questions (see page 15 below)

Adequacy of Protection Against Risks:

Informed Consent: We will obtain written informed consent for all persons in this study. We do this through a process of continuous informed consent, such that research assistants will remind subjects throughout their initial intake and interview process that participation is voluntary, and they can seek to opt-out and/or speak with a counselor at any time. If there is any concern that the client is unable to give full informed consent due to anxiety, we will not pursue further questioning and discount the interview.

ART will be provided through the Hannan-Crusaid Treatment Centre in Gugulethu per usual routine. When a subject agrees to participate, he or she will sign a consent form drafted in the appropriate language (English or Xhosa). Participants will be asked to summarize the study and to explain the reasons why they want to participate, prior to seeking a signature. If there are cultural literacy reasons why a signature is not appropriate, individuals will be allowed to mark consent forms with an X. At this point, any misunderstandings regarding procedures, risks, or benefits can be clarified. Individuals will be provided with information on how to contact the study staff to report adverse events or other concerns associated with the study. Approval of the consent form will be sought from both the Partners Human Research Committee and the Ethics Committee at the University of Cape Town in South Africa prior to study initiation.

Measures to Protect Against Risk:

Anxiety due to a new HIV diagnosis – Social workers will be available on site free of charge for any subject needing additional counseling. If there is any concern that the client is unable to give full informed consent due to anxiety, we will not pursue further questioning and discount the interview.

Potential loss of confidentiality - To ensure confidentiality of all participants, all data will be coded by subject number. We will store NHLS data in separate files and will only link data by subject number. Data will be stored in Research Electronic Data Capture (REDCap), which is a secure, web-based application for building and managing online surveys and databases.³ REDCap Software is supported by Partners Healthcare. [name] has used this database previously, because of the rigorous standards set to maintain privacy and security. All transactions are fully encrypted, and logins use secure authentication. It is widely used in the academic research community: the REDCap Consortium is a collaborative, international network of more than 900 institutional partners in over 70 countries, with more than 100,000 total end-users employing the software for more than 100,000 ongoing research studies. Interviewers and support staff will be trained on procedures for maintaining privacy and will sign a pledge of confidentiality. Risks to subjects are minimized through informed consent, strict confidentiality, and HIV counseling provided at GCHC.

Planned procedures for protecting against fatigue - Interviews will last 45-60 minutes. Regular breaks will be scheduled throughout the session. Additionally, subjects will be informed that they can take a break or stop at any time. Staff will be well-trained and supervised under the direction of experienced clinical researchers.

Discussion of sensitive topics- Efforts will be made to minimize discomfort by assuring that interviewers are well-trained and that they will inform participants beforehand about the nature of the questions and assure participants of privacy. The interviewer will be available after the interview to debrief with the participant if s/he is in any way concerned by the nature of the questions. Routine demographic questions will be asked first, followed by more personal questions. Participants will be informed that they have the right to decline participation in the study, to refuse to answer any questions, or to withdraw at any time without adverse consequences. In addition, researchers will be sensitive to any potential concerns regarding mistrust of providers. We will review all data collection materials with our community advisory board to guide our research. The CABs have helped to foster a culture of trust and mutual understanding with the community and to ensure that the research conducted through the Desmond Tutu HIV Foundation respects the values and cultural differences among those who participate. As an added level of protection for clients, we will ensure that the research assistant working on this project is not a healthcare provider on staff at the clinic.

Ensuring access to ART - We will offer “minimal wait” referrals to either medical providers or counselors at every study encounter to minimize structural barriers to ART initiation. A “minimal wait” visit means that the participant will be referred to a medical provider and/or counselor and will be the next individual seen as needed. We recognize that this enhanced referral strategy will produce a Hawthorne effect by decreasing the impact of our planned intervention. This, however, does not represent a significant change from clinic policies that are currently in place, and is consistent with the overarching philosophy of GCHC and The Desmond Tutu HIV Foundation. In addition, it fulfills our ethical obligation to provide access to lifesaving therapy, and is a conservative bias towards the null.

Ensuring Minimization of Psychological Distress – We will provide the following to participants:

1. Participants will be informed that the assessments include questions about sensitive behaviors (e.g., mental health, drug use, non-adherence), and that they can decline to answer any questions with which they are uncomfortable.
2. Procedures for emergency and nonemergency situations will involve the interviewer informing the SA SCO of any such incidents of distress so that s/he can monitor compliance with distress-related protocol.
3. Participants who experience mild to moderate distress will be referred to the clinic mental health staff for counseling. Because the study will take place near the Hannan Crusaid Treatment Centre, we will be able to make immediate referrals as needed to health care providers.

All surveys will take place in a private location and all data will be stored in a secure location accessible only to study researchers. Any study participant has the option of stopping the survey or intervention. Study participants may ask to be de-enrolled at any time. Research staff will remind participants that participation is completely voluntary and they may choose to withdraw from the study.

EXPECTED BENEFITS

Subjects may become more aware of the importance of HIV treatment and therefore initiate ART sooner, with a potential decrease in morbidity and mortality, as well as a decreased risk of transmission to HIV-uninfected partners. They may also benefit from knowing that their participation may help others like them in the future. Otherwise, there are no known direct benefits to subjects.

EQUITABLE SELECTION OF SUBJECTS

Our inclusion criteria do not exclude any group of persons other than women who are currently pregnant and persons under 18 years of age. These groups are not included in the proposed research study because of the study's recruitment site, which refers pediatric and pregnant clients to more specialized care facilities that may better suit their needs.

While English is the recognized language for commerce and science in South Africa, there are over 11 official languages. In Cape Town, Xhosa and Afrikaans are the most commonly spoken languages. However, Xhosa is the most widely spoken language among the population likely to enroll in this study (i.e., specific location of clinic). The consent form and subsequent surveys/questionnaires will be translated by a local multilingual research assistant into Xhosa.

RECRUITMENT PROCEDURES

Our goal is to recruit ART-eligible, treatment-naive persons living with HIV (PLWH) who have undergone testing at GCHC within the last three to six months and have failed to initiate ART. Based on our preliminary studies, we estimate about 8-10 participants will be recruited per month for our randomized control trial (RCT). Therefore, we estimate it will take 12 months to fully recruit our full sample for our RCT. This will allow approximately 18 months to implement the full intervention.

In order to identify and reach this population, we initially will approach individuals who gave permission to contact for future research in our previous study, "Examining the Correlates and Outcomes of HIV Treatment Refusal in an Adult South African Cohort"; University of Cape Town Human Research Ethics Committee HREC REF: 328/2014 Approved on 11 August, 2014.

Should we need to approach more people than agreed to future research in this previous study, we will recruit from the Gugulethu CHC, Nyanga CHC, Vuyani clinic and Gugulethu clinics. The study team has a known relationship with these clinics. We will apply to the City of Cape Town and the Provincial research committees for permission to recruit at these sites. In addition, this study has been presented to the Emavundleni Community Advisory Board (the CAB used by the Desmond Tutu HIV Foundation) for community participation and buy-in.

If participants sign our initial consent form, our research assistant (RA) will contact eligible PLWH to assess their interest in participating in the study. We will use medical records and pharmacy on site (80-85% of participants) and data from the NHLS to track whether an ART-eligible individual has started treatment within six months of testing. While NHLS only provides lab data, we will be following participants for a total of 6 months (three months of intervention plus an additional four months post intervention), and will be able to monitor standard labs that are sent within four to six months on treatment.

For participants who qualify and agree to enroll in our study, we will obtain written informed consent in English or Xhosa for all study phases. We will do this through a process of **continuous informed consent**, such that research assistants will remind participants throughout their initial intake and interview process that participation is voluntary, and they can seek to opt-out and/or speak with a counselor at any time.

This protocol is an iterative pilot intervention where all participants will be part of the intervention. This step will inform and further develop/modify our full intervention of up to 90 where participants will be randomized to intervention or control after baseline data collection (1:1). We will ensure gender balance throughout the study. ART will be provided through the Department of Health (DOH) treatment center per standard of care.

Specific inclusion criteria and eligibility criteria to participate in the study are as follows:

- HIV-infected persons eligible for treatment under current South African treatment guidelines and choosing not to initiate ART within three months of learning their eligibility;
- Antiretroviral therapy (ART) naive;
- Age 18 years or older;
- Capable of providing informed consent; and
- Live within 60 kilometers of the Hannan Crusaid ART clinic.

Specific exclusion criteria disqualifying an otherwise eligible person from participating in this study include:

- Anyone previously on ART;
- Age less than 18 (initiation patterns and determinants may differ from those of adults);
- Residence greater than 60 kilometers from the clinic (due to prohibitive cost of following participants);
- Unable to provide informed consent (e.g., due to intoxication or mental incapacity); and

- Women who report current pregnancy at the time of consent (women pregnant at time of ART initiation may have different motivations of initiating ART and adherence patterns).

Each study participant will be reimbursed a total of 100 Rand per survey completed – for a total of 300 Rand. In addition, they will receive a 200 Rand bonus for completing all three surveys. If participants are randomized to the intervention arm, they will receive 20 Rand per session to cover their transport costs.

CONSENT PROCEDURES

Consent is a step-wise process: First, prospective participants consent to be contacted regarding participation in the study; then we explain the study and its risks; and finally, participants must sign the consent form in order to participate in the study.

The interviewee does not have to participate in the interview at that time, if it is inconvenient for them. We will obtain consent in a private location and it will either be obtained by the study principal investigator (PI) or by a research assistant directly trained and working with the PI. There is no time-table for consent, and a study participant can agree to consent and be part of the study at any time. Oral consent serves as an assurance that the required elements of informed consent have been presented orally to the participant or the participant's legally authorized representative.

All forms used in this study, including the consent form, have been translated into English and Xhosa, the two official languages most-widely used in the study area. The local research assistants will explain any risks that a reasonable person would want to understand regarding their potential participation in this study.

DATA AND SAFETY MONITORING

The risks associated with this study are less complex than those of larger, multisite phase I or II trials. Thus, the data and safety monitoring plan for this study will be limited. We will assume primary responsibility for data safety and monitoring. In this research, the primary risk to subjects is social harm due to loss of confidentiality associated with the survey and motivational interviewing process and possible physical harm (e.g., acts of physical violence directed at people who have been disclosed as HIV-infected). In this study, there is risk of embarrassment and stigma (e.g., being questioned about sexual behavior).

We have set up several mechanisms to ensure confidentiality of subjects. All surveys will occur in a private space. Contact with the interviewer will only occur with prior written consent from the subject. The nature of any information that might be disclosed is included as part of this consent. All paper files will be in locked file cabinets, and electronic files will be stored in password-protected files. Furthermore, both paper and electronic files will be identified only by the subject's identification number. The Project Manager will retain identifying information linking subjects to their study identification number off site in a locked cabinet only accessible to her, and myself. Finally, I will review confidentiality policies and procedures with all staff on an annual basis. We will monitor confidentiality practices on a weekly basis. I will notify University of Cape Town and Partners' institutional review boards of any breaches in confidentiality or other adverse events attributable to this study within ten days of the event.

MONITORING AND QUALITY ASSURANCE

A project manager will be involved in the oversight of the study and will continually monitor the data. The principal investigator and the research assistants will monitor the data. Weekly quality assurance checks will be performed by the research assistants to ensure validity and integrity of the data.

All study staff will go through a training program to promote standardized and objective collection of participant information. To ensure fidelity of data collection, I will use random supervisor contact (the Project Manager working with me) to verify the accuracy of survey data. Data will be managed in a relational database. Questionnaires are automatically read by optical character recognition into a Microsoft SQL-server database; human verification of key text fields provides a second level of quality assurance. Data entry verification will include algorithms that automatically check completed forms for missing, out-of-range, or inconsistent values. Aberrant entries are reported immediately on the project's website so that the original interviewer can reconcile the problem immediately. This method of rapid error reporting and resolution by field staff quickly results in improved interviewer accuracy. Databases will be maintained in an NT-operating system in a password protected partitioned drive, and backed-up daily and quarterly (24G NT Backup). A relational database will link socio-demographics, behavior, and survey results by a unique subject identifier and date.

PRIVACY AND CONFIDENTIALITY

All surveys will be performed privately at a mutually convenient time and location. Research records will be kept confidential to the level allowed by the law. To ensure confidentiality of all participants, all data will be coded by subject number. Physical records will be kept in locked cabinets and will be accessible only to study personnel. Computerized records will be kept on a secure, password-protected computer server via REDCap. Any identifying information that links a patient to HIV status or laboratory records shall be stored only in REDCap and not in paper form. REDCap keeps all linked data password-protected and encrypted to prevent loss of confidentiality.

All Support staff (includes research assistants) will be trained on procedures for maintaining privacy and confidentiality and obtaining informed consent. All SMS messages will be arranged during baseline to ensure no identifying information or stigmatizing messages are sent. Treatment Ambassadors will be trained on procedures for maintaining privacy and confidentiality; however, their role is verbal and they will not have access to written data. We will not disclose study information to anyone other than the participant.

SENDING SPECIMENS/DATA TO RESEARCH COLLABORATORS OUTSIDE PARTNERS

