Patient navigation can be used as an effective technique for improving linkages-to-care. Data are emerging regarding the impact of patient navigation as an effective strategy for improving engagement in care. Navigation is an efficacious, flexible, individualized approach to assist PLHA in identifying and overcoming barriers to health services. We hypothesize that patient navigation can complement the other facets of our intervention, including social support, and MI techniques, to help PLWH identify barriers to entering care and devise solutions by optimizing the use of available resources.

RESEARCH DESIGN AND METHODS

Overall Strategy for Proposed Study Design: We propose to iteratively develop and conduct a pilot multi-component, socio-behavioral intervention aimed at promoting early and enduring uptake of treatment among PLWH in SA, who otherwise would not avail themselves of the benefits of freely available treatment. We will conduct our work through an ongoing partnership between US and SA academicians, with input from a community advisory board (CAB) consisting of adult members of the community and community-based therapeutic counselors at The Desmond Tutu HIV Foundation. The proposed study is based on our formative research. We will hire and train TAs, who will be identified as "successful" people living with HIV, who will then serve in multiple capacities, including delivering the MI intervention through individual sessions, while providing peer-support and peer navigation. We intend to perform our intervention over three months, a duration that has proven efficacious in our prior domestic research. Our goal is to provide eligible participants with in-person one-on-one weekly contact with their assigned TA as well as weekly phone check-ins. Before pilot testing the intervention, we will perform a phase of iterative development.

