Intervention Fidelity and Treatment Ambassadors Qualifications: We will achieve consistency in intervention implementation through proper hiring and training, and ongoing supervision and monitoring. We will select Treatment Ambassadors who are comparable to those who might lead the program in community settings. They must be PLWH, have a record of proven attendance and leadership in their community, have completed high-school, and

possess relevant interpersonal skills for MI (e.g., empathy, warmth, and respect for individual differences/choices).

Facilitators, Training, and Fidelity: Three Treatment Ambassadors will be trained. Each TA will engage with 12-14 participants. TAs will complete a comprehensive training and demonstrate cultural and treatment education competency, including: basic knowledge of HIV; confidentiality and HIPAA regulations; crisis intervention; referral resources; cultural and social issues; and substance abuse assessment. The training will be led by [name] (Co-Investigator) and a Xhosa-speaking co-facilitator ([name], who has worked with [name] previously in South Africa on MI interventions). [name] and [name], with assistance from Drs. [name] and [name] (Co-investigator), will conduct a four- day training. The training will cover program content, MI style, and administrative and study details. After Drs. [name] and [name] introduce the study design and protocol, [name] will begin the MI training, using materials (e.g., videos, exercises) from the Motivational Interviewing Network of Trainers. The training will consist of one day of initial MI training. [name] and [name] will then lead the group through simulated program sessions on the second day. The third day will focus on the intervention training that Drs. [name] and [name] will lead. Facilitators will then role-play potential questions and challenging situations and practice all program activities and components on the fourth day. Facilitators will conduct simulated sessions with each other and be rated for proficiency in both program content and MI by [name]. TAs must meet proficiency for at least three consecutive sessions prior to beginning the sessions.

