We will use a blocked randomization design based on gender, with a goal of equal representation of males and females. Participants will be randomized to the standard of care (referral to initiate ART) or the intervention arm. A computerized random-number generator will be used to formulate an allocation schedule; participants will be given their assigned allocations within sealed opaque envelopes. The RA enrolling patients will be blinded to the randomization assignment. Upon completion of the baseline questionnaire, the randomization assignment will be revealed. For participants randomized to the TAP arm, the RA will notify the TA, who will come to meet the participant immediately upon completion of the survey. We will seek to prevent control group contamination (i.e., controls being influenced by what the intervention group is learning). For contamination to threaten the ability to detect intervention effects, statistical models suggest that $\geq 30\%$ of the control group must receive the equivalent of a full-strength intervention², which we believe to be highly unlikely. Nevertheless, we will survey participants about possible contamination (e.g., whether they discussed this study with community members) upon study completion.

Data collection.

Primary Outcome. ART initiation – Assessed at the completion of the intervention (month 3) and monthly through 6 months post-intervention. This will be measured through both self-report, medical records at GCHC, and accessing data through the NHLS.

Demographics. We will collect baseline demographic data, and HIV clinical data (diagnosis date, clinical history, most recent CD4 count).

Laboratory testing. Standard protocol at the testing center is testing of the participant's blood to determine HIV status and CD4 and participant eligibility. This is done routinely already at GCHC.

Self-Report Measures. We will administer two sets of surveys to the pilot groups (baseline and at completion of the intervention) to test survey questions and tracking procedures. Our current

study in Gugulethu utilizes an interviewer-administered survey that has been shown to be feasible. Participants will complete the baseline survey before randomization. Code numbers will link data over time. Intervention participants who drop out of the program will be encouraged to complete all surveys.

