Primary data analysis will be an intent-to-treat analysis, which includes all randomized participants. Of note, every attempt will be made to continue assessing participants even if they drop out of treatment. In addition, we will replicate all analyses with the completers only. The hypothesis that The Treatment Ambassador Program will yield higher rates of ART initiation by the completion of the intervention will be tested using Fisher's exact test; the treatment effect estimate will be summarized in terms of a relative risk and 95% confidence interval. Any baseline demographic or clinical variables identified as necessary covariates in preliminary analyses will be included in a logistic regression analysis that examines the main effect of treatment condition on the rates of ART initiation.

Power/Sample Size Considerations. Because this is a pilot study, power considerations for testing null hypotheses are somewhat less relevant than having adequate degrees of freedom to estimate treatment effects with a reasonable degree of precision for potential use in a future fully-powered trial. However, for completeness, we present a summary of the power analyses for the primary hypothesis below. With a sample size of up to 45 per treatment group, the probability is greater than 80 percent that the study will detect a difference of 25% in the percent who initiate ART. This is based on the assumption that the percent who initiate ART in the control group is approximately 10%, as seen in our prior research in SA. Thus, the study is adequately powered to detect medium-to-large effect sizes (corresponding to a relative risk = 3.5) for the primary outcome. Finally, allowing for a dropout or attrition rate anticipated to not be greater than 10%, we plan to recruit a total of up to 90 participants (45 per group) to ultimately guarantee our complete sample of 80 participants. This proposed sample size provides more than sufficient degrees of freedom to obtain a precise estimate of the primary outcome event rate and a preliminary relative risk

comparison of the two treatment groups, even when allowing for up to 10% loss to follow-up. If promising results are detected, these data will provide an estimate of the reliability of the intervention effect to inform power calculations for a larger RCT.

Process Evaluation to Examine the Feasibility and Acceptability of the Intervention.

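### Three ambassadors deliver the whole intervention arm, yet no result is planned by ambassador; intervals for the arm's initiation rate and the survey differences ignore ambassador variation, while the relative-risk interval is hardly affected

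*Combined protocol and SAP*

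**What the plan says.** Delivery: the Facilitators, Training, and Fidelity paragraph states "Three Treatment Ambassadors will be trained. Each TA will engage with 12-14 participants". The Overall Strategy paragraph promises "in-person one-on-one weekly contact with their assigned TA as well as weekly phone check-ins". The randomization paragraph states "Participants will be randomized to the standard of care (referral to initiate ART) or the intervention arm", so only one arm has ambassadors.

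Analysis: the primary analysis is intent-to-treat with Fisher's exact test, and "the treatment effect estimate will be summarized in terms of a relative risk and 95% confidence interval". If baseline imbalance calls for it, a logistic regression with baseline covariates is added. The process evaluation section compares seven survey measures at 6 months, using a bootstrap interval for the between-arm difference in means and a permutation test. None of these paragraphs has an ambassador term, an ICC, a design effect or a result by ambassador.

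Use of the results: the power paragraph ranks estimation for a future trial above hypothesis testing. It claims that the sample is more than large enough to estimate the event rate precisely, and says of promising results that "these data will provide an estimate of the reliability of the intervention effect to inform power calculations for a larger RCT". The planned next trial is multi-site.

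**The concern.** Participants who share an ambassador may have more similar outcomes than participants who do not. One unusually effective or ineffective ambassador affects a third of the arm. An interval that treats the participants as independent then describes delivery by these three people and leaves out the variation expected when others deliver the program. The next trial will use other ambassadors, so that variation is part of the reliability the pilot is meant to gauge. Without initiation counts by ambassador, a reader of the pilot could not tell an effect shared by all three from one produced by a single ambassador.

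**Working it through.** **Inputs from the documents.** Up to 45 per arm; 10% initiation in controls; a 25-point difference, so 35% with the intervention (relative risk 3.5); three ambassadors. At 45 in the arm, m = 45/3 = 15 per ambassador. The stated 12–14 each gives 36–42.

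**Assumptions.** ICC 0.01 to 0.10. Since the between-ambassador SD is √(ICC × 0.35 × 0.65), this means 4.8, 10.7 and 15.1 points at ICC 0.01, 0.05 and 0.10. Two-sided 5% level. Log-scale Wald interval for the relative risk and Wilson interval for the arm's rate, because the plan names no method. Bootstrap resampling of individuals, and equal variances in the two arms for the survey scores.

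**1. The plan's power figure.** Normal approximation with independent participants and pooled rate 0.225:
- SE under the null = √(2 × 0.225 × 0.775/45) = 0.0880
- SE under the alternative = √((0.35 × 0.65 + 0.10 × 0.90)/45) = 0.0840
- power = Φ((0.25 − 1.96 × 0.0880)/0.0840) = 82.2%, which reproduces the stated figure of above 80%.

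The planned test is Fisher's. Its exact two-sided power for the same inputs is 76.1%, before any clustering.

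**2. Design effect, intervention arm only.** 1 + (m − 1) × ICC = 1 + 14 × ICC. This is 1.14, 1.70 and 2.40, so the effective size of the arm is 45/1.14 = 39.5, 45/1.70 = 26.5 and 45/2.40 = 18.75.

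**3. Relative risk.** The variance of the log relative risk is 0.65/(45 × 0.35) + 0.90/(45 × 0.10) = 0.0413 + 0.2000. Controls supply 0.2000/0.2413 = 83% of it and are not clustered. At ICC 0.10 it becomes 0.0413 × 2.40 + 0.2000 = 0.299, and the interval around 3.5 goes from 1.34–9.17 to 1.20–10.22.

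**4. Survey mean differences.** With equal variances the true SE is √((1 + design effect)/2) times the unadjusted one: 1.03, 1.16 and 1.30. Approximate coverage is 2Φ(1.96/ratio) − 1.

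**5. Coverage and power.** Lines for the arm's rate, the relative risk and Fisher power come from beta-binomial simulation (three ambassadors with 15 participants each against 45 independent controls, 10% versus 35%, at least 200,000 runs), averaged over ambassadors. The survey line uses the formula in step 4.

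| Output | ICC 0 | 0.01 | 0.05 | 0.10 |
|---|---|---|---|---|
| Coverage, intervention-arm initiation rate | 95.9% | 94.4% | 88.0% | 80.6% |
| Coverage, survey mean difference | 95% | 94% | 91% | 87% |
| Coverage, planned relative risk | 96.9% | 96.7% | 95.8% | 94.6% |
| Fisher power | 76% | 75% | 72% | 70% |

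With 13 per ambassador, inside the stated 12–14, relative-risk coverage is 96.6%, 96.4%, 95.7% and 94.8%.

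**The case against.** The strongest reply is that the plan's primary interval does not fail. This stands. A reader might infer from the nesting that the 95% interval for the relative risk is too narrow, but at the design rates its coverage stays near or above nominal over the whole assumed range. Coverage figures of 88% and 82% can be produced for a Wald risk-difference interval, but the plan does not report that interval.

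A reader might also infer that clustering is why the power claim fails. Most of the shortfall (82% to 76%) comes from using a normal approximation for a trial that will use Fisher's test; clustering takes a further 1 to 6 points. The fall to 58% at ICC 0.10 that a clustering-adjusted normal calculation gives belongs to a test the plan does not use.

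Nor do the documents support a claim of inflated type I error. At 10% in both arms the simulated rejection rate reaches 4.2–4.3% at ICC 0.05 and 6.6–6.7% at ICC 0.10, but only if the ambassadors have real, offsetting effects (SD √(0.10 × 0.10 × 0.90) = 9.5 points at ICC 0.10). That is not the null of no effect on anyone.

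The protocol also requires proficiency before sessions start, fidelity coding, weekly supervision and closer monitoring after a lapse. These make the upper end of the ICC range harder to presume. They do not show that it is zero, because no planned output relates ambassador to ART initiation. Contacts and fidelity are recorded, so some information on ambassadors will exist; what is missing is the outcome by ambassador.

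Finally, this is a pilot focused on acceptability and feasibility, and an interval conditional on the delivered intervention is legitimate. That stands too, provided the report says so.

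**Conclusion.** The point holds as a minor one. Treating the intervention arm as independent does not bias the estimate, does not invalidate Fisher's test for its strict null, and does not materially harm the planned relative-risk interval. It does overstate precision for the intervention-arm initiation rate and for the survey mean differences once the results are taken beyond these three ambassadors.

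These sizes depend on the assumed ICC range, on 15 participants per ambassador and on the design rates of 10% and 35%. The arm-rate result also assumes that the precision claimed for the event rate extends to the intervention arm, for which the plan specifies no interval.

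**What to change.** In the primary analysis paragraph, with matching text for the survey comparison:

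1. Record the assigned ambassador for every intervention participant, and report starters over assigned for each of the three. The available text gives no rule for matching participants to ambassadors, so this table is descriptive.
2. Report the intervention-arm initiation rate and the survey mean differences with a sensitivity table that multiplies the intervention-arm variance by 1 + (m − 1) × ICC for ICC 0.01, 0.05 and 0.10. Show the relative risk there only for completeness. Fixed values are preferable to an estimate, because three ambassadors leave 2 degrees of freedom.
3. State that the unadjusted intervals describe these three ambassadors, and carry the same ICC range into the larger trial's sample size.
4. When restating power, give the Fisher figure (about 76% at 45 per arm) and note the further loss of about 1 to 6 points from clustering.

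The cost is plan wording and two small tables. No extra participants, visits or instruments are needed, since ambassador assignment is already part of delivery. The downside is somewhat wider sensitivity intervals and a lower stated power.
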